3.7 Treatment assignment and treatment groups

Because N01349 is an open-label, single-arm study, subjects will not be randomized to any treatment groups. The first 6 subjects meeting the eligibility criteria will be assigned to the Exploratory Cohort. Subsequent subjects will be assigned to the Confirmatory Cohorts.

3.8 Center pooling strategy

There is no differentiation by center in this study, i.e. the data will be analyzed from all centers together.

3.9 Coding dictionaries

Medical history (if available) and adverse events (AEs) will be coded using the Medical Dictionary for Regulatory Activities (MedDRA) version 18.1. Medications will be coded using

the World Health Organization Drug Dictionary (WHO-DD) version September 2017. Medical procedures will not be coded.

3.10 Changes to protocol-defined analyses

Table 3.1: Changes to protocol-defined analyses

Protocol-defined analyses	New analyses
Primary cause of seizure subgroups for the efficacy analysis are changed from the protocol defined: 1. HIE, hemorrhage, or infarction 2. CNS malformations; 3. CNS infections; 4. undetermined causes	Primary cause of seizure subgroups based on the eCRF categories: 1. HIE 2. Ischemic stroke 3. Intracranial hemorrhage 4. Epileptic encephalopathy/genetic epilepsy 5. Intracranial infection 6. Brain malformation 7. Inborn error of metabolism 8. Undetermined cause 9. Other

4 STATISTICAL/ANALYTICAL ISSUES

4.1 Adjustments for covariates

Not applicable for this study.

4.2 Handling of dropouts or missing data

There will be no specific imputation of missing data except for missing dates and/or times for concomitant medication and AE.

The handling of missing dates and times for seizures if applicable will be discussed during the Data Evaluation Meeting (DEM).

4.2.1 Handling of prior and concomitant medications with missing data

Any medications with incomplete start and end dates/times will be handled according to the following rules for classification as prior and concomitant and for the calculation of relative study days. Such imputations will only be performed for these classifications and calculations; in the listings all data will be shown as recorded on the electronic Case Report Form (eCRF).

Imputation of Partial Start Dates:

- If only the month and year are specified and the month and year of first dose is not the same as the month and year of the start date, then use the 1st of the month.

- If only the month and year are specified and the month and year of first dose is the same as the month and year of the start date, then use the date of first dose.
- If only the year is specified, and the year of first dose is not the same as the year of the start date, then use January 1 of the year of the start date.
- If only the year is specified, and the year of first dose is the same as the year of the start date, then use the date of first dose.
- If the date is completely unknown, then use the date of first dose.

Imputation of Partial End Dates:

- If only the month and year are specified, then use the last day of the month.
- If only the year is specified, then use December 31 of that year.
- If the date is completely unknown, do not impute the stop date.

There will be no imputation of any other missing data.

4.2.2 Handling of adverse events with missing data

Any AEs with incomplete onset and outcome (end) dates/times will be handled according to the following rules for classification as treatment-emergent. Such imputations will only be performed for these classifications; in the listings all data will be shown as recorded on the eCRF.

- If only the month and year are specified and the month and year of first dose is not the same as the month and year of onset, then use the 1st of the month.
- If only the month and year are specified and the month and year of first dose is the same as the month and year of onset, then use the date/time of first dose.
- If only the year is specified, and the year of first dose is not the same as the year of onset, then use January 1 of the year of onset.
- If only the year is specified, and the year of first dose is the same as the year of onset, then use the date/time of first dose.
- If the AE onset date is completely unknown, then use the date of first dose.
- Imputations for missing end dates/times will not be performed for classification as treatment-emergent as this is not required.

Adverse events with missing severity or causality will be regarded as ‘severe’ and ‘related’ respectively for the tabulations. There will be no imputation of any other missing data. Any AE with additional missing data that prohibits classification for a given tabulation will be excluded from that tabulation.

In case of uncoded AEs, these AEs should be designated as “UNCODED” at all MedDRA levels, and such AEs will be included in summary tables and subject listings based on this classification.

4.2.3 Handling of dropouts or missing efficacy data

For subjects who drop out during the Evaluation Period, the number of hours from the start of the Evaluation Period to the time of withdrawal (in hours) will be considered for analysis. Subjects in the Confirmatory Cohorts who are withdrawn or are switched over to another AED treatment prior to the Evaluation Period or are administered >1 dose of rescue medication (including BZDs) following the first 3 hours after initial BRV treatment started will be considered BRV non-responders.

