5.1.2 Confirmatory Cohorts

For the Confirmatory Cohorts, enrollment will only start after the dosing of BRV is determined based on the PK findings of the Exploratory Cohort and an existing PK model from N01263. A total of at least 36 subjects without adequate seizure control after receiving one or more of the following AEDs prior to or at the time of enrollment: PB, MDZ, PHT, LEV (≤60 mg/kg/day), or LDC (first-line, second-line, or subsequent treatment, which may have started prior to the subject's admission into the study site; dose and dosing regimen at the Investigator's discretion) will enter the Confirmatory Cohorts. The AED treatment can be continued if the subject is on a stable dose for at least 1 hour at the time the first BRV infusion is initiated.

Three consecutive Confirmatory Cohorts (n=12 each) are planned; each cohort must have at least 2 subjects undergoing hypothermia treatment. A PK and safety data review will be performed by

the DMC after completion of each of the 3 Confirmatory Cohorts. Based on the DMC meeting held on 05 Nov 2020, the BRV dose and frequency selected for the Confirmatory Cohorts is 1mg/kg bid (2mg/kg/day). Based on data from the Confirmatory Cohorts, the BRV dose may be further adjusted in a staggered approach as determined by the DMC. During the PK and safety data review of data from the first and second Confirmatory Cohorts, the recruitment of subjects into subsequent cohorts will continue.

The study periods for the Confirmatory Cohorts are as follows:

Screening Period: from signing and dating of the written ICF up to initiation of the first BRV dose.

- The Screening Period starts up to 36 hours prior to the first administration of BRV. Phenobarbital, MDZ, PHT, LEV ($\leq 60\text{mg/kg/day}$), or LDC may have been administered prior to the subject's enrollment into the study and/or at a location other than the study site.
- Baseline Period (included in the Screening Period):
 - For subjects with **intermittent ENS**: at least 1 hour prior to entering the Evaluation Period
 - For subjects in **status epilepticus**: up to 30 minutes prior to entering the Evaluation Period. At least 15 minutes of continuous seizures, or 50% of cumulative seizure activity during a 30-minute interval are to be confirmed on EEG before the administration of BRV can start.

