5.4 Rationale for study design and selection of dose

5.4.1 Rationale for study design

The current accepted medical practice (ie, standard of care) for neonatal seizures is initial treatment with PB with rapid progression to treatment with MDZ for patients without adequate seizure control after 2 doses of PB. In more than 50% of subjects, seizures are not controlled after first-line treatment with PB or other AEDs, and subsequent treatment with additional AEDs does not significantly improve seizure control (van Rooij et al, 2013b; Castro Conde et al, 2005; Boylan et al, 2004; Painter et al, 1999). Thus, study N01349 was designed for a flexible treatment of ENS, and only those subjects who do not have adequate seizure control with previous AED treatment will be permitted to continue in the study.

As the patient population of neonates with ENS is limited, the 2-step design of this study will allow confirmation (or adjustment) of dosing based on results from the first step (Exploratory Cohort) and evaluation of BRV efficacy in the second step (Confirmatory Cohorts). This adaptive design allows confirmation of dose and collection of PK, safety, and efficacy data, thereby potentially providing rapid access to alternative treatment in neonates.

The frequency, voltage, and morphology of the discharges may change within an individual seizure and between seizures in an individual neonate. At enrollment, subjects must be at least 34 weeks of CGA. In addition, term neonates up to 27 days of PNA and preterm neonates up to 40 weeks of CGA and 27 days of PNA can be enrolled. Neonates undergoing hypothermia treatment (eg, for the treatment of HIE) will also be enrolled.

Although newer AEDs are efficacious for the treatment of seizures in adults and older children, limited progress has been made in the treatment of neonatal seizures (Pressler et al, 2015; Pressler and Mangum 2013; Tulloch et al, 2012). Thus, clinical studies to assess the efficacy and safety of new treatment options in neonates are warranted.

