6 SELECTION AND WITHDRAWAL OF SUBJECTS

6.1 Inclusion criteria

To be eligible to participate in this study, all of the following criteria must be met:

1. An Independent Ethics Committee (IEC)-approved written ICF is signed and dated by the parent(s) or legal representative(s).
- 2a. Confirmation on VEEG of ≥ 2 minutes of cumulative ENS or ≥ 3 identifiable ENS prior to entering the Evaluation Period (ENS is defined as a seizure lasting for at least 10 seconds on VEEG), despite receiving previous AED treatment for the treatment of electroencephalographic seizures.

The occurrence of ENS during an up to 1-hour period must be confirmed either by the local or central VEEG reader prior to drug administration. Preferably, the central VEEG reader should confirm the required ENS.

3. Subject is male or female and must be at least 34 weeks of CGA. In addition, term neonates up to 27 days of PNA and preterm neonates up to 40 weeks of CGA and 27 days of PNA can be enrolled.
4. Subject weighs at least 2.3kg at the time of enrollment.
5. Subjects with or without concomitant hypothermia treatment.

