13.7 Handling of dropouts or missing data

For subjects who dropped out during the Evaluation Period, the number of hours from the start of the Evaluation Period to the time of withdrawal (in hours) will be considered for analysis. Subjects in the Confirmatory Cohorts who started another AED, increased the dose or frequency of administration of an AED ongoing at the time the first BRV infusion started, or are switched to another AED, or have been administered any rescue medication for the treatment of ENS during the first 3 hours after initiation of BRV treatment will be considered BRV nonresponders.

The impact of missing data on the assessment of the main secondary efficacy variable will be evaluated with sensitivity analyses with further details to be included in the SAP.

No imputation of missing values associated with an individual date or visit is planned for the safety analysis, with the exception of partial date information for AEs and concomitant medications, in order to determine whether they are treatment emergent.

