2.3.2 Confirmatory Cohorts

For the Confirmatory Cohorts, enrollment will only start after the dosing of BRV is determined based on the PK findings of the Exploratory Cohort and an existing PK model from N01263. A total of at least 36 subjects without adequate seizure control after receiving one or more of the following AEDs prior to or at the time of enrollment: PB, MDZ, PHT, LEV (\leq 60mg/kg/day), or LDC (first-line, second-line, or subsequent treatment, which may have started prior to the subject's admission into the study site; dose and dosing regimen at the Investigator's discretion) will enter the Confirmatory Cohorts. The AED treatment can be continued if the subject is on a stable dose for at least 1 hour at the time the first BRV infusion is initiated.

Three consecutive Confirmatory Cohorts (n=12 each) are planned; each cohort must have at least 2 subjects undergoing hypothermia treatment. A PK and safety data review will be performed by the DMC after completion of each of the 3 Confirmatory Cohorts (12 subjects each), but no later than intervals of 6 months. During the PK and safety data review of data from the first and second Confirmatory Cohorts, the recruitment of subjects into subsequent cohorts will continue.

The study periods for the Confirmatory Cohorts are as follows:

- Screening Period: from signing and dating of the written ICF up to initiation of the first BRV dose.

The Screening Period starts up to 36 hours prior to the first administration of BRV. Phenobarbital, MDZ, PHT, LEV ($\leq 60\text{mg/kg/day}$), or LDC may have been administered prior to the subject's enrollment into the study and/or at a location other than the study site.
- Baseline Period (included in the Screening Period):
 - For subjects with **intermittent ENS**: at least 1 hour prior to entering the Evaluation Period.
 - For subjects in status epilepticus: up to 30 minutes prior to entering the Evaluation Period. At least 15 minutes of continuous seizures, or 50% of cumulative seizure activity during a 30-minute interval are to be confirmed on EEG before the administration of BRV can start.

As soon as subjects are considered to be in status epilepticus, steps required for the preparation of the initial BRV infusion can be initiated (eg, assignment of BRV kits through interactive response technology [IRT] and the dilution of BRV solution for iv infusion), even if the required EEG recording is not completed by that time.

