3.2.2.2.3 Evaluation Period

Evaluation Period starts when the subject receives first dose of BRV infusion and will last for 96 hours. If subjects do not benefit from BRV treatment after 96 hours of BRV administration, BRV administration will be stopped and replaced by another AED; however, the subject's participation in the study will continue.

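### SAP 4.2.3 ties BRV non-response to an AED switch before the first BRV dose; the clause is either wrong or empty, and it conflicts with SAP 8.1.1 and Protocol 13.7.

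*SAP*

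**What the plan says.** SAP 4.2.3, on dropouts and missing efficacy data, gives a list of subjects to be treated as BRV non-responders. It includes Confirmatory Cohort subjects who are withdrawn or who "are switched over to another AED treatment prior to the Evaluation Period". The sentence also names those given more than one dose of rescue medication after the first 3 hours. It is not limited to any endpoint.

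SAP 3.2.2.2.3 fixes the time point: "Evaluation Period starts when the subject receives first dose of BRV infusion and will last for 96 hours".

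On entry, SAP 2.3.2 describes babies "without adequate seizure control after receiving one or more of the following AEDs prior to or at the time of enrollment", given as "first-line, second-line, or subsequent treatment". Protocol 5.1.2 has the same rule and adds that this treatment may have begun before admission to the site. Inclusion criterion 2a requires seizures on VEEG "despite receiving previous AED treatment for the treatment of electroencephalographic seizures".

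Two other places set the non-responder rule. Protocol 13.7 covers an AED that is started, increased or switched, or rescue that is given, "during the first 3 hours after initiation of BRV treatment will be considered BRV nonresponders". SAP 8.1.1 likewise places the switch and rescue triggers in the first 3 hours after BRV starts. Neither mentions AED changes before BRV. SAP 8.2.1 takes the numerator of the main secondary variable from Section 8.1. SAP 3.10, which lists changes from the protocol-defined analyses, does not mention the 4.2.3 rule.

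**The concern.** A non-responder rule for BRV should act on what happens after BRV is given. This clause acts on what happened before. Taken at its word, it classifies a baby by treatment history, and that history is one the trial admits: seizures that persist after one or more AEDs, at any line of treatment. The clause sets no limit on how far back a switch may lie.

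At stake is the responder rate. Protocol 13.5.1 compares its 95% CI, for all Confirmatory Cohorts combined, with a historical responder rate and reads the result as efficacious, not efficacious or inconclusive. A rule that turns true responders into failures lowers that interval. Even if nobody intends to apply the clause, the SAP holds two different rules for one status and no order of precedence. In an open-label trial, that choice should not be left until the data have been seen.

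**Working it through.** The documents state no power, sample-size calculation or expected response, so there is no planned figure to reproduce. The check is first of meaning, then of possible size.

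**What the clause can mean**

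1. The Evaluation Period starts at the first BRV dose (SAP 3.2.2.2.3), so an event before it precedes all BRV exposure.
2. *Literal reading:* the switch is from one standard-of-care AED to another. Entry allows this (SAP 2.3.2, Protocol 5.1.2), so an eligible baby could be caught.
3. *Switch away from BRV:* this is how the SAP uses the term elsewhere. SAP 2.3.2 speaks of switching over from BRV, and SAP 8.3.1 derives the variable as stopping iv BRV and starting another AED. This cannot happen before the first BRV dose, so the clause catches nobody.
4. *The withdrawn limb:* the FAS is drawn from the Safety Set, which requires at least one BRV dose (SAP 3.6.1, 3.6.2). A baby withdrawn before the Evaluation Period is not in the efficacy analysis, so this limb is empty if the same timing applies to it.

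**Size if 4.2.3 were applied literally**

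Inputs:
- n = 36, the minimum for the Confirmatory Cohorts (SAP 2.4).
- p = true responder rate, assumed 50%.
- s = share switched between AEDs before BRV. The documents do not give it, so it is varied from zero.
- Response is assumed independent of switching.
- Intervals are Clopper-Pearson, because the SAP names no CI method.

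Formula: responders counted = n × p × (1 − s).

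| Situation | Calculation | Rate | Exact 95% CI |
|---|---|---|---|
| s = 0, or SAP 8.1.1 governs, or the clause means leaving BRV | 36 × 0.5 × 1 = 18 | 18/36 = 50% | 33–67% |
| s = 1/3 | 36 × 0.5 × 2/3 = 12 | 12/36 = 33% | 19–51% |
| s = 1/2 | 36 × 0.5 × 1/2 = 9 | 9/36 = 25% | 12–42% |

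The highest rate attainable under the literal clause is 1 − s: for example, 50% if 18 of 36 were switched, even if every baby responded.

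**Effect on the CI rule, under the same assumptions**

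Take an assumed historical rate of 30%. The lower limit exceeds it only with at least 17/36 responders. With p = 50%, the chance of that is 69.1% at s = 0, 15.1% at s = 25% and 0.3% at s = 50%. The benchmark, p and s are all assumptions.

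**The case against.** The strongest reply is that the operative derivation is sound. SAP 8.2.1 sends the main secondary numerator to Section 8.1, and SAP 8.1.1 confines switch and rescue failures to the first 3 hours after BRV. The percent-change rule in SAP 8.1.5 has no pre-BRV condition, and the sensitivity analysis in SAP 8.2.3 also places switches and rescue after BRV initiation. The rest of the 4.2.3 sentence concerns rescue after the first 3 hours, which lies outside the main variable's window. A programmer working from Section 8 would get the main variable right. This stands, and it is why the possible effect starts at zero.

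A reader might infer something stronger: that the trial selects babies who have moved between AEDs, so that eligible babies fail before their first dose. The documents do not support that. Entry requires inadequate control after at least one AED; it permits a move to another AED but does not require one. Protocol 5.4.1 describes usual care as phenobarbital "with rapid progression to treatment with MDZ for patients without adequate seizure control after 2 doses of PB", but does not say that phenobarbital is stopped, and an added drug is not necessarily a switch. Under Protocol 5.1.2 an earlier AED may continue on a stable dose. On the SAP's own use of the term, the clause may catch nobody.

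The wording also looks like residue. The log for Protocol Amendment 3 shows nearly the same text in Section 13.7 being replaced. That explains the clause and makes a deliberate choice unlikely. It does not remove the clause from the current SAP, where it applies to every endpoint and no section is said to take precedence.

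**Conclusion.** The clause is defective on any reading: wrong if literal, empty if it means leaving BRV. It conflicts with Protocol 13.7 and SAP 8.1.1 and is not declared in SAP 3.10. What is established is an internal conflict over who counts as a non-responder, not a demonstrated bias in the main secondary result.

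The size runs from no effect, if SAP 8.1.1 governs or no baby was switched, to a loss proportional to the share switched before BRV. In the illustration, 50% becomes 33% with one third switched and 25% with half. Those figures rest on an assumed true response of 50%, independence of response from switching, and literal use of 4.2.3. This should be fixed before database lock.

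**What to change.** In one edit to SAP 4.2.3:

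- Delete the clause on subjects withdrawn or switched before the Evaluation Period.
- For the main secondary variable, cross-refer to SAP 8.1.1 and Protocol 13.7: an AED started, increased or switched, or rescue given, in the first 3 hours after BRV initiation.
- State that AED changes before the first BRV dose, including during the Baseline Period, do not by themselves determine responder status. Naming Baseline matters, because a rule covering only changes before Baseline would leave that interval undefined.
- Reconcile the wording in the same sentence that allows one dose of rescue with Protocol 13.5.1, which allows none for the other efficacy variables. Protocol 10.1 words the rule for the other secondary variables in the opposite direction and should be settled at the same time.

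The cost is a short SAP amendment. It needs no new data and no change to trial conduct.

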4.2.4 Handling of study medication with missing data

No imputation should be performed for missing study medication start dates. This field on the eCRF should not be partial or missing.

For partial or missing date of last dose of study medication, the following imputation rules will be applied for the purpose of calculating overall exposure:

- If the day is missing (but month and year available), impute the last dose date as the minimum of the last day of the month or the date of last contact reported on the trial termination CRF; if day and month are both missing (only year available), impute the last dose date as the minimum of the last day of the year or the date of last contact on the trial termination CRF.
- If a subject died and has a partial or missing last administration date, the date is to set to the date of death. If there is a partial date of last dose and the month/year are prior to the month and year of the date of death, follow partial date imputation rules.
- If the last dose date is completely missing and no information could be obtained from data cleaning exercises, the last dose date should be imputed as the date of last contact per the study termination CRF. A review of the data for subjects with completely missing last dose dates should be performed to ensure that the imputation does not result in an unrealistic value for duration of exposure.
- If the time is missing, set the time to 00:00

Imputed date of last dose dates should only be used for calculation of the duration of exposure. The date as recorded on the eCRF should be presented in subject data listings (no imputed dates should be included in subject data listings).

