5.1.3 Study duration per subject

The maximum study duration per subject is expected to be up to 75 days (Screening Period [including Baseline Period (Confirmatory Cohorts only)], Evaluation Period, BRV Extension Period, Down-Titration Period [Confirmatory Cohorts only], and Safety Follow-Up Period). In the event that a long-term study is not available at the time of a subject's planned transition, the maximum study duration for subjects who remain in the study for up to 90 days of PNA and do not enter the long-term study will then be up to 130 days (90 days of PNA, up to 1 week for the Down-Titration Period, and up to 33 days for the Safety Follow-Up Period). The individual study duration will be shorter depending on the type of cohort to which subjects will be assigned, the age at enrollment, and the decision to enter the BRV Extension Period.

The maximum BRV exposure per subject is expected to be up to 42 days, which comprises up to 4 days during the Evaluation Period (depending on type of cohort), up to 28 (+7) days of PNA during the BRV Extension Period, and up to 1 week during the Down-Titration Period for subjects in the Confirmatory Cohorts only. For subjects who remain in the study for up to 90 days of PNA and do not enter the long-term study, maximum BRV exposure per subject is expected to be up to 97 days (up to 90 days of PNA and up to 1 week for the Down-Titration Period).

All subjects who do not continue into the long-term study will proceed to the Safety Follow-Up Period, and a visit will occur 30 ± 3 days after the final dose of BRV.

The end of the study is defined as the date of the last visit of the last subject in the study.

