2.3.3 Study duration per subject

The maximum study duration per subject will be up to 75 days (Screening Period [including Baseline Period (Confirmatory Cohorts only)], Evaluation Period, BRV Extension Period, Down-Titration Period [Confirmatory Cohorts only], and Safety Follow-Up Period). The individual study duration will be shorter depending on the type of cohort to which subjects will be assigned, the age at enrollment, and the decision to enter the BRV Extension Period.

The maximum BRV exposure per subject will be up to 42 days, which comprises up to 4 days during the Evaluation Period (depending on type of cohort), up to 28 days (+7 days) of postnatal age during the BRV Extension Period, and up to 1 week during the Down-Titration Period for subjects in the Confirmatory Cohorts only.

All subjects who do not continue into the long-term study will proceed to the Safety Follow-Up Period, and a visit will occur 30 ± 3 days after the final dose of BRV.

The end of the study is defined as the date of the last visit of the last subject in the study.

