3.2.2.6 Safety Follow-Up Period

Subjects will proceed to the Safety Follow-Up Period once they complete the Down-Titration Period. The end of the Safety Follow-up Period will be defined as last contact to the subject, which will be the Follow-Up visit. This visit will occur 30 ± 3 days after the final administration of BRV.

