10.1 Extent of exposure

The duration of BRV exposure, is defined as the start date and time of last administration of study medication (BRV) minus the start date and time of first administration of study medication (BRV) plus duration of dosing interval (12 hours, however the dosing interval may be adjusted if results point into that).

The duration of iv BRV exposure during the Evaluation Period will be displayed in hours. The duration of exposure of iv BRV and oral BRV solution during the BRV Extension Period will be displayed in days.

The date and time of last administration of study medication is the maximum date and time from the CRFs “Study Medication Administration (Infusion)” and “Study Medication Administration (Oral Solution)”.

Exposure as categorical parameter will be summarized as number of doses received (1 dose, > 1 dose) and continuous parameter (in hours or days). For the continuous parameter, descriptive statistics for the duration of exposure to study medication in hours or days will be presented. For the number of doses, the number and percentage of subjects who received 1 dose and >1 doses will be summarized. Handling of study medication missing data is described in [Section 4.2.4](#).

Exposure as a continuous parameter will be categorized (>0-12 hours, >12-24 hours, >24-48 hours, >48-72 hours, >72-96 hours, >96 hours – 14 days, >14 days) by study periods for

Exploratory, individual Confirmatory Cohorts and for overall combined Confirmatory Cohorts for the SS.

The following listings will be provided:

- study medication administration,
- exposure to study medication BRV infusion, and
- exposure to study medication BRV oral solution.

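### SAP 4.2.4 replaces a wholly missing last-dose date with last contact, which for Safety Follow-Up subjects is 27 to 33 days too late; its month-end and 00:00 rules also distort exposure, with no substitute value

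*SAP*

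**What the plan says.** SAP 10.1 builds exposure from two time points and a constant. "The duration of BRV exposure, is defined as the start date and time of last administration of study medication (BRV"), less the start of the first administration, plus a 12-hour dosing interval. The result is summarised as a continuous variable and in categories cut at 12, 24, 48, 72 and 96 hours and at 14 days.

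SAP 4.2.4 supplies the last dose when it is not fully recorded:

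- **Date entirely missing, nothing recovered by cleaning:** "the last dose date should be imputed as the date of last contact per the study termination CRF". The affected subjects are then reviewed to "ensure that the imputation does not result in an unrealistic value for duration of exposure".
- **Day missing:** "impute the last dose date as the minimum of the last day of the month or the date of last contact". If only the year is known, year end replaces month end.
- **Death:** the date of death is used, unless a partial date points to an earlier month.
- **Time:** "If the time is missing, set the time to 00:00".

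SAP 3.2.2.6 (Confirmatory Cohorts) says: "The end of the Safety Follow-up Period will be defined as last contact to the subject, which will be the Follow-Up visit". SAP 3.2.2.1.4 says the same for the Exploratory Cohort. Both place that visit 30 ± 3 days after the final administration. For subjects who go on to the long-term study, SAP 3.2.2.1.3 and 3.2.2.2.4 tie last contact to the end of the Extension Period instead.

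**The concern.** In a subject followed to the Follow-Up visit, last contact is separated from the last dose by a fixed drug-free interval of about a month. Using one as a stand-in for the other adds that interval to exposure. The direction and approximate size of the error are known in advance from the SAP's own definitions.

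The neighbouring rules have related faults. Month end takes the latest possible day and carries no review. Midnight takes the earliest possible time and has no lower bound at the first dose.

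Exposure is part of how the safety data are read. The Evaluation Period lasts 48 or 96 hours, and each Confirmatory Cohort is planned with 12 subjects, so a single month-long error is visible in a cohort table.

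**Working it through.** **Inputs.** Exposure = (start of last dose − start of first dose) + 12 h (SAP 10.1). Follow-Up visit at 27 to 33 days after the last dose (SAP 3.2.2.1.4, 3.2.2.6). Up to 8 doses in the Confirmatory Evaluation Period (Protocol 8.2.2). Assumption: first dose at 10:30, as in the SAP 3.2.1.1 examples, and doses 12 hours apart.

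**The plan's own figures.** SAP 2.3.3 gives a maximum exposure of 42 days: 28 + 7 + 7 = 42. It gives a maximum study duration of 75 days: 42 + 33 = 75. The difference, 33 days, is the longest gap from last dose to Follow-Up visit, so the plan itself separates the two dates by that interval.

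**Date entirely missing.** The time is then missing too, so the last dose is placed at 00:00 on the visit date. With 8 doses, the last starts 84 h after the first, at 22:30 on the fourth day. True exposure is 84 + 12 = 96 h. Imputed exposure is 84 + 24d − 22.5 + 12 h, where d is the visit day:

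| Visit day d | Imputed exposure | Overstatement |
|---|---|---|
| 27 | 721.5 h = 30.1 days | 26.1 days |
| 30 | 793.5 h = 33.1 days | 29.1 days |
| 33 | 865.5 h = 36.1 days | 32.1 days |

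Over all clock times and the whole visit window, the overstatement runs from 26.0 to 33.0 days. A single dose (12 h) with a day-30 visit becomes 30.1 days. Eight doses followed by a one-week down-titration (11 days) become 37.1 to 43.1 days. One error of about 30 days adds 30/12 = 2.5 days to the mean of a 12-subject cohort, or 30/36 = 0.8 days to the combined mean.

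**Day missing.** If the true last dose falls on day k of a 30-day month, month end is 30 − k days late. Averaged over k = 1 to 30 this is 14.5 days. The maximum is 29 days, or 30 in a 31-day month. Example: last dose on 8 January at 22:30, Follow-Up visit between 4 and 10 February. Month end is the earlier date, so the last dose becomes 31 January at 00:00, which is 22.1 days late, and exposure goes from 4.0 to 26.1 days. The limit at last contact seldom helps, because last contact is itself at least 27 days after the dose.

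**Time missing.** Doses at 10:30 and 22:30 on the first-dose day: true exposure is 12 + 12 = 24 h. With 00:00 it is −10.5 + 12 = 1.5 h, and the last dose precedes the first. On a later day the effect is only a shortfall of less than 24 h. Three doses from 22:30 to 22:30 the next day give 24 + 12 = 36 h in truth and 1.5 + 12 = 13.5 h under the rule, one category lower.

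**Check of the repair.** Last contact minus 30 days lies within 3 days of the true date for any visit inside its window. A cap at last contact minus 27 days lies 0 to 6 days after it. In the January example the cap falls on 8 to 14 January instead of 31 January.

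**The case against.** The strongest reply is that the rule will hardly ever be used. It comes after data cleaning. Staff record the start and end of every infusion (Protocol 7.7), and exact dosing times go into the eCRF (Protocol 9.1). SAP 10.1 already takes the latest entry across the infusion and oral-solution forms. The Follow-Up visit is scheduled from the final dose, so a site that held it on time knew that date. Listings show recorded dates, and PK and efficacy are untouched. Month end is also the SAP's convention for medication end dates (SAP 4.2.1).

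Most of this stands, and it keeps the point small. The realistic source of gaps is oral dosing at home, recorded by parents in a diary, rather than supervised infusion. It does not rescue the rule: a last resort should still give a sensible value. The review is a genuine safeguard, but it covers only entirely missing dates and names nothing to put in place of a rejected value. SAP 4.2.4 also does not tell the programmer to fall back on the last dated record.

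Three stronger readings are tempting and not supported:

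- **The review works to an outdated ceiling.** SAP 2.3.3 says "The maximum BRV exposure per subject will be up to 42 days", while Protocol 5.1.3 says that for subjects kept to 90 days of age "maximum BRV exposure per subject is expected to be up to 97 days". But the review in SAP 4.2.4 cites no numerical limit and does not refer to SAP 2.3.3. The difference is a version matter, since the SAP states that it rests on Protocol Amendment 6. A 97-day limit would also let more of these wrong values through.
- **Midnight always reverses the order of doses.** It does so only on the first-dose calendar day.
- **Every subject is exposed to the month-long error.** Rollovers and deaths follow other definitions.

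**Conclusion.** The point holds as a minor error in stated rules. For a subject who completes Safety Follow-Up and whose last-dose date is entirely missing, exposure is overstated by 26 to 33 days, enough to move a 12- to 96-hour exposure above 14 days. A date lacking its day is up to about 30 days late and unreviewed. A missing time costs up to 24 hours and reverses dose order on the first-dose day.

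This rests on three assumptions: the Follow-Up visit is held inside its window; last contact on the termination form is that visit; and the imputed date feeds the tabulated durations. The last is not fully settled: SAP 4.2.4 speaks of overall exposure, whereas SAP 10.1 categorises by study period and does not say how an imputed date is divided between periods.

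The documents do not show how many subjects would be affected; it may be none. A reader might infer that the trial's safety or efficacy conclusions are at risk. They are not: imputed dates are confined to duration of exposure, and all analyses are descriptive.

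**What to change.** Amend SAP 4.2.4 before database lock:

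1. Take the last administration documented on the infusion or oral-solution form, in the dosing diary or through drug return.
2. If none settles the date and the subject had a Safety Follow-Up visit, impute last contact minus 30 days. Leave the rules for rollovers and deaths as they are.
3. For partial dates in such subjects, cap the imputed date at last contact minus 27 days.
4. Never impute a last dose earlier than the last recorded dose.
5. Replace 00:00 with the preceding recorded dose time plus the dosing interval used in SAP 10.1, kept within the recorded date. In the two-dose example this restores 22:30 and 24 h.
6. Extend the plausibility review to partial dates, and have it apply steps 1 to 4 when it rejects a value.

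The cost is a paragraph of SAP text and a few lines of programming. No new data are needed.
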